### ***Pulmonary function imaging – chest X-ray***

A chest X-ray (posterior-anterior and lateral views) will be performed at screening and approximately every 6 months since the first infusion at sites, except for the patients in Germany (since Germany radiation board did not allow this); for further details of timing, please refer to the protocol.

Chest X-rays will be collected at the site and sent to a medical imaging core laboratory where they will be digitized (if not already done at the site), coded, and read by a third-party reader blinded to patient number and study visit. The lung fields will be scored subjectively for the degree of ILD - interstitial, reticular, nodular density, consolidation and pleura thickening of the right and left lungs separately according to the following criteria:

- 0 = No infiltrative lung disease.
- 1 = Mild (affecting 1% to 25% of the lung volume).

- 2 = Moderate (affecting 26% to 50% of the lung volume).
- 3 = Severe (affecting 51% to 100% of the lung volume).

Mean score across both lungs = Sum of 2 lung scores / 2

### ***Treadmill ergometry***

Treadmill ergometry is performed at screening and approximately every 6 months since the first infusion; for further details of timing, please refer to the protocol. Completion of the assessment may depend upon patient cooperation.

Treadmill ergometry assessments will include maximum workload (watts), percent predicted maximum workload (%), working time (min), maximum heart rate (breaths/min), percent predicted maximum heart rate (%), maximum O2 saturation (%), maximum respiratory rate (breaths/min), maximum ventilation (L/min), maximum tidal volume (mL), percent predicted maximum O2 uptake (mL/min), maximum O2 uptake (%), maximum CO2 output (mL/min), and maximum respiratory exchange ratio.

### ***Fasting lipids (including lipoproteins of interest)***

Fasting lipids evaluations are done at screening and approximately every 3 months since the first infusion. The parameters include: total cholesterol, LDL, HDL, VLDL, triglycerides, apolipoprotein B, apolipoprotein A1, and lipoprotein [a]. A derived parameter of non-HDL will be evaluated as follows: total cholesterol minus HDL (10).

### ***Hematology***

Platelet counts and hemoglobin are considered efficacy parameters. The hematology and hemogram sample collection schedule has been described under platelet count which is a secondary endpoint ([Section 2.1.4.2](#)). The rest of the hematology parameters, such as hematocrit, white blood cell counts (WBC), and red blood cell count are part of safety endpoints. Hematology samples evaluate all hematology parameters, while hemogram samples evaluate only platelet, hemoglobin and total and deferential WBC.

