9.1.4.9 Hematology

Although hemoglobin level, platelet count, and white blood cell count are part of the standard safety laboratory assessments ([Section 9.2.2](#)), they will also be analyzed at screening, Week 52, and at yearly visits (at the time points in [Section 1.2.1.1](#) and [Section 1.2.1.2](#), respectively) as part of the analysis of secondary (platelet counts) and tertiary (hematology) efficacy endpoints.

As specified in [Section 1.2](#), at screening, Week 52, and at yearly visits, the mean of 2 preinfusion samples taken at least 24 hours and up to 2 weeks apart will be used for white blood cell count, platelet count, and hemoglobin.

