11.5.5.3 Clinical laboratory tests

Observed values and changes from baseline to study time points will be summarized. All laboratory values will be classified as normal, above normal, or below normal based on normal ranges provided by the laboratory. Frequencies of clinically significant abnormal values and shifts from baseline to study time points will be summarized. Patient listings of biomarkers will be provided.

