## **2.4.5 Analyses of efficacy endpoints**

Efficacy data will be analyzed by randomized treatment group in mITT population at scheduled time point. The statistical analyses will compare olipudase alfa versus placebo within PAP; the difference between two treatment groups is calculated as olipudase alfa minus placebo.

Primary analyses period is 52 weeks.

Efficacy analyses will use mITT population unless specified otherwise. This will include patients who used rescue therapy, but their data after rescue will NOT be included in the analysis. Sensitivity analyses including data beyond rescue therapy may be undertaken if appropriate.

Baseline values are generally the latest value before the first infusion of the study drug, except for platelets and hemoglobin which are part of hematology parameters; for hematology parameter baseline definition, please refer to [Section 2.6.1](#).

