#### ***Platelet counts***

The MMRM model as used in the primary analysis of spleen volume under primary efficacy endpoints will be used to compare treatment groups for percentage change in platelet count from baseline to Week 52, using mITT population. Data collected at the quarterly visits will be included in the MMRM model. Supportive summary in mITT-C population will be provided.

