### **2.4.6.2 Laboratory data**

For parameters that are reported as below the quantification limit (BQL), the results often convey a clinically meaningful change. Therefore, a numerical value is necessary to be imputed for including these in descriptive statistics calculations. For all these parameters either the lower limit of quantification (LLOQ) is available in the database, or the result is reported as <xx. The numeric value for results of BQL will be imputed as LLOQ/2; the numeric value for results reported as <xx will be imputed as xx/2.

In hematology, platelets and hemoglobin are part of efficacy parameters, and have been described under [Section 2.1.4](#). For the rest of hematology parameters, the baseline will be defined the same way ([Section 2.6.1](#)), and any visit which is scheduled to collect two samples pre-infusion for WBC, the average of the two values will be used as pre-infusion value.

Observed values, change from baseline and percent change from baseline to scheduled study time points will be summarized in separate groups of hematology (excluding hemoglobin and platelets which are considered efficacy parameter, hence the analyses have been described in [Section 2.4.5](#)), liver function tests, coagulation, etc. as described in [Section 2.1.5](#) (excluding lipids which have been described as part of efficacy, [Section 2.4.5.7](#)). Summary plots over time will also be provided as needed.

Laboratory values will be classified as normal, above normal, or below normal based on normal ranges when provided by the laboratory. Shifts from baseline to scheduled time points, any time during the on-treatment period and the last available value, in the abnormality of any parameters will be provided.

PCSA values for clinical chemistry, hematology and liver function tests (provided in [Section 7.2](#)) during the study (from first infusion to last available observation) will be summarized. PCSA values for hematology, liver function test and clinical chemistry parameters will be provided in separate listings.

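### SAP 2.4.6.2 leaves the 24-hour post-infusion platelet and hemoglobin values without a specified observed or change-from-baseline summary, although the protocol keeps both as safety laboratory tests

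*SAP*

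**What the plan says.** The protocol gives these tests two roles. Section 9.1.4.9 opens "Although hemoglobin level, platelet count, and white blood cell count are part of the standard safety laboratory assessments" and then adds an efficacy analysis on top. Section 11.5.5.3 says of the safety laboratory tests: "Observed values and changes from baseline to study time points will be summarized". It makes no exception for any hematology parameter.

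The SAP makes the roles exclusive. Section 2.1.4.3 says "Platelet counts and hemoglobin are considered efficacy parameters", and of the others "The rest of the hematology parameters, such as hematocrit, white blood cell counts (WBC), and red blood cell count are part of safety endpoints". Section 2.4.6.2 then plans observed, change and percent-change tables for "hematology (excluding hemoglobin and platelets which are considered efficacy parameter, hence the analyses have been described in" Section 2.4.5. In 2.4.5.2 the platelet analysis is a mixed model for repeated measures (MMRM) of percentage change: "Data collected at the quarterly visits will be included in the MMRM model". Section 2.4.5.7 gives hemoglobin the same treatment. Section 2.4.5 also says of rescued patients "but their data after rescue will NOT be included in the analysis".

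SAP 2.1.5.3 nevertheless still lists hemoglobin and platelets, with a 24-hour sample, among the laboratory safety variables.

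**The concern.** The 24-hour sample exists to show what happens soon after an infusion. For hematocrit, WBC and the other blood counts, the SAP tabulates that value and its change from baseline by arm. For platelets and hemoglobin it removes the table and points to a section that never mentions the sample.

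These are the two counts named in the rescue criteria (protocol 8.1.6), and bleeding is an event of other interest in SAP 2.1.5.1. A modest, consistent post-infusion fall during dose escalation is the kind of signal that a mean-change table shows and a threshold table may not.

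**Working it through.** The plan states no figure on this point, so the check is a comparison of sections and a count.

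**Where the 24-hour values go in the SAP**

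- Observed and change tables (2.4.6.2): platelets and hemoglobin are excluded by name.
- Efficacy analyses (2.4.5.2, 2.4.5.7): MMRMs on quarterly visits. The 24-hour sample is not named.
- Shift tables (2.4.6.2): kept for any parameter, with no exclusion.
- PCSA summaries and listings (2.4.6.2): kept for hematology. The common rules in 2.4.6 count every evaluation in the treatment-emergent period, so 24-hour values enter.
- Liver tests, for contrast (2.1.5.3): pre-infusion values are efficacy, and the 24- and 48-hour values are safety. No such sentence is written for platelets or hemoglobin.
- Declared departures (1.5): seven items, including multiplex biomarkers reclassified from efficacy-and-safety to safety only. The platelet and hemoglobin exclusion is not among them.

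The SAP was written against amended protocol 11. The amendment history for versions 12 to 15 lists no change to protocol 9.1.4.9 or 11.5.5.3, so the comparison is not an artefact of versions.

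**Number of time points affected in the PAP**

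- Weeks 0, 2, 4, 6, 8, 10, 12, 14 and 16 (protocol 1.2.1.1, hematology footnote): 9.
- Weeks 26, 38 and 52 (protocol 1.2.1.2, hematology footnote): 3.
- Total: 9 + 3 = 12 per patient. For 36 patients without dropout, 12 × 36 = 432 samples.
- Only Weeks 14, 26, 38 and 52 are quarterly visits, so 12 − 4 = 8 of the 12 fall at visits outside the MMRM, whichever sample the model is taken to use.

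**What the remaining outputs can and cannot show**

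- Platelets (SAP 7.2): the low criterion needs a value below 100 and a 20% fall. A fall from 140 to 105 is (140 − 105)/140 = 25%, but 105 is not below 100, so nothing is flagged.
- Hemoglobin (SAP 7.2): a fall of 20 g/L or more from baseline is flagged at any level, so the gap is smaller than for platelets.
- Shift tables: a patient already below normal at baseline shows no shift after a further fall.

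**The case against.** Several stronger readings are tempting, and the documents do not support them.

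- *The two parameters have left safety reporting.* They have not. Shift and PCSA outputs remain, and SAP 2.1.5.3 still lists both as safety variables.
- *Falls to rescue level could go unseen.* For platelets they could not. Entry requires a count of at least 60 and rescue needs one below 30. From an eligible count the fall exceeds (60 − 30)/60 = 50% and the value is below 100, so the PCSA criterion is met. The laboratory rescue criteria also require a repeat low value after about two weeks, so an isolated 24-hour dip does not qualify.
- *Data after rescue disappear.* SAP 2.3.2 says that PAP data after rescue will be provided separately for the rescue population.
- *Most of the hematology data are wasted.* There are 11 post-baseline pre-infusion and 12 post-infusion PAP time points. If the MMRM uses 4 pre-infusion values, 19 of 23 (83%) lie outside it. That says little about safety reporting, because an efficacy model need not use escalation visits.
- *WBC needs its own MMRM.* The protocol promises no model for tertiary hematology, and 2.4.6.2 already summarises WBC values and changes. What is missing is a declaration that a parameter named for efficacy in protocol 9.1.4.9 is now safety only.

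The best remaining objection is that part of the case rests on silence. The platelet and hemoglobin models do not say pre-infusion, whereas the liver-test model does. SAP 2.4.5.8 and 2.4.6.14 plan PAP+ETP summaries at longitudinal time points in general terms. The accurate statement is therefore that no such summary is specified, not that none could be produced. This does not remove the point: the exclusion in 2.4.6.2 is explicit, and general wording elsewhere does not clearly reverse it. Reading the 24-hour sample into the two-sample averaging rule in SAP 2.1.4.2 would be worse. It would mix post-infusion values into a secondary endpoint, whereas protocol 9.1.4.9 averages two pre-infusion samples.

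**Conclusion.** The point holds in a limited form. A stated rule takes platelets and hemoglobin out of the observed and change tables that the protocol promises for safety tests, and the section it points to does not specify a replacement for the 24-hour values. Twelve scheduled PAP time points per patient are left to shift and PCSA outputs. This conflicts with protocol 9.1.4.9 and 11.5.5.3, sits badly with the SAP's own safety list and liver-test split, and is undeclared in SAP 1.5.

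The count assumes the planned schedule, with no rechallenge, missed visit or dropout. The consequence is incomplete safety description, mainly for platelets. No primary or secondary test is affected, and nothing here shows that a harmful fall would go unreported.

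**What to change.** 1. In SAP 2.1.4.3 and 2.1.5.3, apply the liver-test split to platelets and hemoglobin: pre-infusion values are efficacy, 24-hour post-infusion values are safety. Leave the 2.4.5 analyses unchanged, but state that they use pre-infusion values.
2. In 2.4.6.2, replace the exclusion with observed and change-from-baseline summaries of both parameters at the scheduled 24-hour post-infusion time points.
3. Show PAP data after rescue separately for the rescue population (2.3.2), and keep values before rescue under the randomised arm. SAP 2.3.2 counts a rescued placebo patient as olipudase alfa-treated, so an ordinary safety-population table would put that patient's placebo-period falls in the olipudase alfa column. SAP 1.5 already moved the exposure summary to the modified intent-to-treat population for a similar reason.
4. In 1.5, declare that WBC is handled as a safety parameter. No model is needed.

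The cost is a few lines of SAP text and two more parameters in an existing table shell. No new data are needed.

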### ***Bone disease assessments***

#### **Bone marrow burden**

An MRI of lumbar spine and bilateral femur is performed at screening and at yearly visits. Three parameters are evaluated for each region: T1 weighted score, T2 weighted score, extent of involvement - femur only, infiltration pattern - spine only. The scale of these results is as follows:

Spine T1 score: 0=slightly hyperintense, 1=isotense, 2=slightly hypointense, 3=hypointense

Spine T2 score: 0=isointense, 1=slightly hyperintense or slightly hypointense, 2= hyperintense or hypointense

Infiltration pattern - infiltration: 0=None, 1=Patchy, 2=Diffuse

Infiltration pattern - fat in basivertebral vein region: 0=Preservation of fat, 1=Absence of fat

Femur T1 score: 0=Slightly hyperintense or isointense, 1=Slightly hypointense, 2=Hypointense  
Femur T2 score: 0=Isointense, 1=Slightly hypointense or slightly hyperintense, 2=Hypointense or hyperintense, 3=Mixed type  
Extent of Involvement: 0=No site involvement, 1=Diaphysis, 2=Proximal epiphysis / apophysis, 3=Distal epiphysis

Total bone marrow burden (BMB) score for each region is derived by adding up the individual scores. Total BMB score is derived by adding the total BMB score of two regions, and ranges from 0 to 16 [0 to 4: mild; 5 to 8: moderate; 9 to 16: marked to severe].

### **Dual-energy X-ray absorption parameters**

Dual-energy X-ray absorption (DXA) of lumbar spine and bilateral femur is performed at screening and at yearly visits. Three parameters are evaluated for each region, and for left and right side separately: Bone mineral density (BMD), T-score and Z-score. The scale of these results is as follows:

BMD: a numerical value in the unit of  $\text{g}/\text{cm}^2$   
T-score: [score  $\geq -1$ ] = Normal, [score  $> -2.5$  to  $< -1$ ] = Osteopenia, [score  $\leq -2.5$ ] = Osteoporosis  
Z-score: [score  $> -2$ ] = Normal, [score  $\leq -2$ ] = Below normal

A total score is obtained by averaging the two side scores within each region.

### ***Bone biomarkers***

Bone-specific Alkaline phosphatase and C-telopeptide levels are evaluated at screening and approximately every 3 months since the first infusion.

### ***Efficacy biomarkers***

Serum chitotriosidase, ligand 18 (CCL-18), and ACE are evaluated at screening and approximately every 3 months after the first infusion of the study drug.

Chitotriosidase values will be normalized prior to study analyses based on the patient's chitotriosidase genotype:

Chitotriosidase genotype	Normalization of chitotriosidase activity
Normal	Reported value to be used
Heterozygous	Value multiplied by 2
Homozygous mutation	Value set to "no value"

### ***Physician's global assessment***

The physician will assess the disease severity of the patient at screening, as mild, moderate, severe. At approximately every six months exposure of the study treatment, the disease severity

will be assessed. At these clinic visits, the investigator will also evaluate the patient's current clinical status compared to screening (baseline) by marking 1 of 7 categories: "marked improvement of daily activities", "moderate improvement of daily activities", "mild improvement of daily activities", "no change", "mild worsening of daily activities", "moderate worsening of daily activities" or "marked worsening of daily activities".

### ***NMR of HDL***

Evaluation of HDL by NMR will be performed at Screening, then every six months since first infusion for 2 years, yearly thereafter.

### ***Liver function via echo-Doppler ultrasound***

Detected signs of portal vein hyperpressure is considered an efficacy measure and will be assessed through liver function via echo-Doppler ultrasound at Screening, Week 52 and Week 104.

## **2.1.5 Safety endpoints**

The safety analysis will be based on the reported adverse events and other safety information, such as clinical laboratory data, vital signs, ECG, etc.

### ***Observation period***

The observation period will be divided into epochs:

- The **screening** epoch (or pretreatment epoch) is defined as the time from the signed informed consent date up to the start of the first infusion of investigational medicinal product (IMP) in the study (excluded).
- The **treatment** epoch is defined as the time from the first infusion of IMP (included) to the end of the study.
  - The treatment epoch for PAP is defined as the time from the first infusion of IMP (included) to:
    1. the time just prior to first infusion in ETP if the patient has an infusion in ETP;
    2. the last date the data are available if the patient has no infusion in ETP.
  - The treatment epoch for ETP is defined as the time from the first infusion in ETP to the end of the study.

Based on these epochs the safety data collected in this study will be classified as pre-treatment and treatment emergent.

The on-study observation period is defined as the time within treatment epoch.

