During the PAP, one rechallenge each will be allowed for doses administered at Week 0 (0.1 mg/kg olipudase alfa or placebo) and at Week 4 (0.3 mg/kg olipudase alfa or placebo). Patients who are unable to tolerate the rechallenge at those doses will be discontinued from the study. If a patient is discontinued due to inability to tolerate rechallenge (ie, a second dose of 0.3 mg/kg olipudase alfa), then an additional patient may be randomized. Any patient who successfully dose-escalates through Week 4, but cannot tolerate study drug infusions at later weeks, will continue in the trial at the Week 4 dose (ie, 0.3 mg/kg olipudase alfa or placebo) until end of study; likewise, any patient unable to tolerate a dose administered during later weeks will receive the HTD even if that dose is less than the target randomized dose and will continue in the ETP at this dose. The minimum active dose administered will be 0.3 mg/kg olipudase alfa.

During the ETP, the same dose-escalation conditions will apply for patients who cross over from the placebo arm during the PAP to the active treatment arm, except that patients unable to tolerate the rechallenge allowed each at Week 54 (0.1 mg/kg olipudase alfa) and at Week 58 (0.3 mg/kg olipudase alfa) will discontinue from the study and will not be replaced.

During the PAP and ETP, in-patient hospitalization will be required preinfusion and for at least 24 hours after the infusion during dose escalation (ie, through Week 16 and Week 70, respectively) and may be required at the quarterly and yearly visits up through the end of Year 2; in-patient hospitalization may be necessary during quarterly and yearly study visits in Years 3 through 5. For all other infusions, patients will be monitored for safety in the clinic for at least 1 hour. All patients will have an end of study/early discontinuation visit within 2 weeks after the last infusion of study treatment. In addition, all patients will receive a follow-up phone call for safety approximately 30 to 37 days after the last infusion of study drug.

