10.3.4 Handling of patients after permanent treatment discontinuation

Any patient who discontinues participating in the study will be contacted by the study investigator to obtain information about the reason(s) for discontinuation and collection of any potential AEs.

If possible, all tests and evaluations listed for the end of study/early discontinuation visit in [Section 1.2](#) are to be carried out within 2 weeks of the last study drug infusion. If a patient fails to return for the necessary visits, then every effort must be made to contact the patient, determine the reason(s) for discontinuation, and record the reason(s) on the e-CRF.

In all cases, the sponsor must be notified of all study terminations as soon as possible and the reason for and date of withdrawal from the study must be recorded in the e-CRF and in the patient's medical record.

In addition, since the primary study comparison is based on intent to treat principle using all randomized patients with any study treatment, missing data, especially the key study assessments during the PAP (12 months) may potentially lead to biased results and challenges in assessing the treatment effect of the study drug. Therefore, all efforts should be made to continue to follow the patients for primary and key secondary endpoints, after the temporary or permanent discontinuation of treatment, in addition to the standard post study safety follow up. If possible, at the minimum, patients should be assessed at their regularly scheduled Week 52 visit (or as close as possible to Week 52) if treatment discontinuation occurred prior to that visit.

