11.5.5.1 Adverse events

Pretreatment AEs will be listed and presented separately from treatment-emergent AEs.

All AEs will be coded using the most recent version of the MedDRA. Adverse event incidence tables will present by system organ class (SOC) (sorted by internationally agreed order) and preferred term (PT), and the number and percentage of patients experiencing an AE. Multiple occurrences of the same event in the same patient will be counted only once in the tables within a treatment period. The denominator for computation of percentages is the safety population within each treatment arm.

All treatment-emergent adverse events (TEAEs), all TEAEs potentially related to study drug, all TEAEs leading to treatment discontinuation and/or study discontinuation, all TEAEs that are IARs, all TEAEs that are SAEs (including those potentially related to treatment), and all AEs with fatal outcome (including fatal TEAEs) will be summarized. The TEAE observation period will be defined as the time from the first infusion of study drug through the end of study visit or 30 to 37 days after the last infusion of study drug, whichever one occurs later.

Detailed listings of TEAEs, SAEs, AESIs, related AEs, and discontinuations due to AEs will be provided and include the randomized treatment arm and olipudase alfa dose of the infusion or placebo before or during the occurrence of the AE, when applicable.

The number of TEAEs and annualized rate, and the number and proportion of patients reporting specific AEs will be tabulated for the overall analyses of AEs.

Separate analyses of AEs may also be conducted by demographic characteristics (eg, age and sex). Adverse events of special interest, such as IARs, and SAEs will be analyzed similarly.

Adverse events of special interest

Detailed listings for AESIs will be provided.

Deaths

The following deaths summaries will be generated:

- Death in nonrandomized patients or randomized and not treated patients
- Treatment-emergent AE leading to death (death as an outcome on the AE CRF page as reported by the investigator) by primary SOC and PT

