### **2.1.5.1 Adverse events variables**

#### ***Adverse event observation period***

- Pretreatment adverse events are adverse events (AEs) that started before the first administration of IMP.
- Treatment-emergent adverse events are adverse events that developed or worsened or became serious during the treatment epoch. These will be defined separately for PAP and ETP.

If due to incomplete information on AE start date/time, the period designation cannot be made unambiguously (for imputation of missing or incomplete dates, please refer to [Section 2.6.2](#)), the AE is assumed to be treatment-emergent (and treatment-emergent in PAP, if so required for assumption).

All adverse events (including serious adverse events and adverse events of special interest) will be coded to a lower-level term (LLT), preferred term (PT), high-level term (HLT), high-level group term (HLGT), and associated primary system organ class (SOC) using Medical Dictionary for Regulatory Activities (MedDRA).

Adverse events are collected from the time of signed informed consent until the end of the study.

Adverse events of special interest include:

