##### **2.4.6.1 Adverse events**

Pre-treatment adverse events are defined as those that have an onset date/time before the first infusion date/time of the patient. Treatment emergent adverse events are those that have an onset date/time in the treatment epoch. Any AE reported in the database with onset date after the end of the treatment epoch will be classified as post-treatment.

The epochs for safety analysis have been defined in [Section 2.1.5](#). Treatment-emergent adverse events will be presented for different periods under different treatment groups as follows (and as appropriate):

1. Adverse events started in PAP treatment epoch, by randomized treatment group.
2. Adverse events started in either PAP or in ETP while taking olipudase alfa. This will be presented by randomized treatment group as well as combined (ie, all patients treated with olipudase alfa).

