## 2.6.6 Statistical technical issues

A sensitivity analysis of the primary efficacy endpoints using a pattern mixture model and different imputations for values missing during the on-treatment period versus values missing after treatment discontinuation is planned. The description of the analysis refers to the DLco endpoint; differences in the implementation for the spleen volume and splenomegaly-related scores are noted. On-treatment period is defined as the time period between the start of first infusion of the study drug up to the day of last infusion in PAP +13 days for patients who did not continue in ETP, or up to the day before first infusion in ETP if the patient continued into ETP.

A pattern-mixture model sensitivity analysis of the percentage change in DLco (% predicted) from baseline to 52 weeks will be conducted, with a different imputation strategy applied for missing DLco values during the on-treatment period and missing DLco values after treatment discontinuation (ie, after the day of last infusion +13 days) based on the following assumptions:

- Patients within 13 days of their last IMP infusion would continue to show benefit from treatment similar to that observed at the scheduled time point. Therefore, DLco values missing during the on-treatment period will be considered “Missing At Random” and imputed using a model estimated using all samples collected on-treatment.
- Patients who stop taking their study treatment will no longer benefit from it in the future, and thus will tend to have DLco values returning to baseline. Thus DLco values missing after treatment discontinuation will be imputed based on a patient’s own baseline value.

Missing DLco values will be imputed 100 times to generate 100 complete data sets. The percent change from baseline to 52 weeks will be derived from observed and imputed DLco at this time point. The complete data sets will be analyzed using an ANCOVA model with treatment group, baseline DLco and baseline age as covariates. The results from the 100 analyses will be combined using Rubin’s formulae.

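### SAP 2.1.5 sets no limit after the last infusion on what counts as treatment-emergent for a patient who never enters the ETP; the protocol's limit is 30 to 37 days, and the change is not declared

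*SAP*

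**What the plan says.** SAP 2.1.5 (Observation period) starts the PAP treatment epoch at the first infusion. It ends just before the first ETP infusion for patients who continue and, for the others, at "the last date the data are available if the patient has no infusion in ETP".

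Several safety analyses depend on that end:

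- SAP 2.1.5.1: "Treatment-emergent adverse events are adverse events that developed or worsened or became serious during the treatment epoch".
- SAP 2.1.5.2 counts a death as on-treatment if it falls in the treatment epoch.
- SAP 2.4.6 counts PCSAs over the treatment-emergent period. SAP 2.4.6.2 to 2.4.6.4 (laboratory, vital signs, ECG) run the PCSA summaries to the last available observation.
- SAP 2.4.6.1 adds a third class: "Any AE reported in the database with onset date after the end of the treatment epoch will be classified as post-treatment".

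Protocol 11.5.5.1 runs the treatment-emergent period from the first infusion "through the end of study visit or 30 to 37 days after the last infusion of study drug, whichever one occurs later", and the protocol synopsis agrees. Protocol 6.1 fixes the timing of the visit: "All patients will have an end of study/early discontinuation visit within 2 weeks after the last infusion of study treatment".

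SAP 1.5 is the list of departures from the protocol's statistical section. It includes another change to Protocol 11.5.5.1 (the annualized event rate moves to the integrated safety summary) but not this one.

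**The concern.** A treatment-emergent table is read as what happened on drug or shortly afterwards. If the window stays open to the last data point, a patient who stops early and is still followed contributes months of off-drug events, deaths and abnormal values to the on-treatment counts. The arms are small, with 36 patients planned at 1:1, so one patient is 1/18 = 5.6 percentage points in a preferred-term incidence.

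The SAP also uses a much shorter period for the same patient elsewhere. SAP 2.6.6 states: "On-treatment period is defined as the time period between the start of first infusion of the study drug up to the day of last infusion". For a patient who does not continue into the ETP, 13 days are then added, and SAP 2.4.4.1 ends PAP exposure at the same 13 days. The 2.6.6 definition serves an efficacy imputation, so it need not match the safety window. It does show that the SAP has no single view of when treatment ends.

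**Working it through.** **The two windows, in days after the last infusion, for a patient with no ETP infusion**

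- Protocol: the later of the end-of-study visit (at most 14) and 30 to 37. max(14, 30) = 30 and max(14, 37) = 37. So 30 to 37 days is the working limit unless that visit is late.
- SAP: the day of the last available data, with no cap.

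**Can data exist beyond day 37?** The documents point both ways.

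- Longer: Protocol 10.3.4 says "all efforts should be made to continue to follow the patients for primary and key secondary endpoints" after treatment stops, at a minimum with a Week 52 assessment if possible. Protocol 10.4.2 continues observation to the end of the study after a premature stop. SAP 2.1.5.1 collects adverse events to the end of the study.
- Shorter: the adverse-event footnotes to the schedules in Protocol 1.2 stop capture at 30 to 37 days after the last infusion. SAP 2.4.6.1.5 says a patient who permanently stops treatment is withdrawn from the study.

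**Size, if data run to a nominal Week 52 visit (assumption)**

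Days from last infusion to Week 52 = (52 − last infusion week) × 7. Excess = that figure − 37.

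| Last infusion | Days to Week 52 | Days beyond day 37 |
|---|---|---|
| Week 10 | 294 | 257 (36.7 weeks) |
| Week 16 | 252 | 215 |
| Week 20 | 224 | 187 (26.7 weeks) |
| Week 26 | 182 | 145 |
| Week 38 | 98 | 61 |
| Week 46 | 42 | 5 |
| Week 48 | 28 | 0 |

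Counted from day 30 instead, the Week 10 case gives 294 − 30 = 264 days (37.7 weeks). A last infusion at Week 48 or later leaves Week 52 inside the protocol window.

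**The post-treatment class.** For a patient with no ETP infusion the epoch ends on the last date with data, and no recorded onset can be later. The class is therefore empty for these patients.

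**Version drift.** The SAP was written against amended protocol 11. The change tables for amendments 12 to 15 list no change to Protocol 11.5.5.1, so a later amendment does not explain the difference.

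**The case against.** The strongest reply is that little may lie beyond day 37. If the schedule footnotes govern, adverse-event capture stops there, and under SAP 2.4.6.1.5 the patient who stops at Week 10 and returns at Week 52 does not arise. Protocol 10.3.4 extends follow-up for efficacy endpoints and sets this beside the standard post-study safety follow-up, so it does not by itself extend adverse-event collection. A longer window also hides nothing, and SAP 2.4.6.1.1 reports treatment-related events separately. All of this bears on how many patients are affected and stands to that extent. It does not remove the conflict, because Protocol 10.4.2 and SAP 2.1.5.1 say otherwise and the epoch itself carries no cap.

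A reader might infer more than the documents support:

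- **That the error falls mainly on olipudase, through intolerance.** Under Protocol 6.1, failing a rechallenge at Week 0 or Week 4 means leaving the study, and intolerance after Week 4 means continuing at a tolerated dose. Neither route leads to long off-drug follow-up. A Week 4 stop is for the same reason a poor example.
- **That the planned 11% gives the number affected.** SAP 1.3 defines it as Week 52 results not being available; a patient who stops drug but attends Week 52 generally has them.
- **That exposure-adjusted rates in this analysis are distorted.** SAP 1.5 moves the annualized rate out of this SAP.
- **That the post-treatment class can never hold an event.** This is true only for patients with no ETP infusion. For the others the epoch ends at end of study, and Protocol 10.4.3 provides for serious events reported after that.
- **That the ETP epoch is equally open.** Protocol 6.2.1 ties ETP completion to the end-of-study visit or the 30-to-37-day call, close to the protocol limit.

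**Conclusion.** Wrong as written. For patients with no ETP infusion, the SAP's treatment-emergent window has no limit after the last infusion, it contradicts Protocol 11.5.5.1, and the departure is undeclared in SAP 1.5.

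The consequence is limited to patients who stop drug in the PAP and have safety data after day 37. For each one the excess depends on the stop date: 36.7 weeks for a last dose at Week 10, 26.7 weeks at Week 20, and none from Week 48. These figures assume safety data up to a nominal Week 52 visit. Week 10 falls within dose escalation, where Protocol 10.1 reduces the discontinuation assessments, so it illustrates the upper range and is not a typical case. The number of affected patients is not stated and may be small, and the direction of any imbalance between arms cannot be determined from the documents.

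**What to change.** 1. In SAP 2.1.5, end the treatment epoch for a patient with no ETP infusion at the later of the end-of-study/early-discontinuation visit and last infusion + 37 days.
2. Align the PCSA windows in SAP 2.4.6 and 2.4.6.2 to 2.4.6.4 with that end.
3. Report later events under the post-treatment class that SAP 2.4.6.1 already provides.
4. If the longer window is preferred, declare it in SAP 1.5 and show the capped table beside it.
5. Reconcile the statements on adverse-event collection and on withdrawal after a stop: the Protocol 1.2 schedule footnotes, Protocol 10.3.4 and 10.4.2, and SAP 2.1.5.1 and 2.4.6.1.5.

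The cost is a few lines of wording and one derivation rule. The downside is that a few late events move from the treatment-emergent table to the post-treatment table; none is lost.
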